**Table KHAA.6.1. General Methods for Statistical Analysis**

Data Type	Purpose	Analysis
Categorical/discrete data	Summary and descriptive analysis	Number of patients with available data (n), either observed or imputed, at the relevant time point, and will be presented as frequency counts and percentages. Percentages will be calculated using the total number of patients in the analysis population included as the denominator. Percentages will generally be presented to 1 decimal place but will not be presented for zero counts.
	Treatment comparison	Logistic regression analysis
Continuous data	Summary and descriptive analysis	Number of observations, mean, standard deviation (SD), standard error of the mean (SEM), median, 1st quartile, 3rd quartile, minimum, and maximum. The minimum and maximum will be reported to the same number of decimal places as the raw data recorded in the database. The mean, first quartile, median, and third quartile will be reported to 1 more decimal place than the raw data recorded in the database. The SD and SEM may be reported to 2 more decimal places than the raw data recorded in the database. Any exceptions will be noted in the programming specifications. P-values for primary and key secondary analyses will be reported to as many decimal places as needed ( $\geq 5$ ).
	Treatment comparison	Analysis of variance (ANOVA), mixed model repeated measures (MMRM), Wilcoxon rank-sum test
Ordinal data	Treatment comparison	Proportional Odds model, Wilcoxon rank-sum test
Time to event data	Treatment comparison	Log-rank test, Kaplan-Meier curves, Cox proportional hazards. As needed: Fine-Gray model, Max-combo test

Note: the detail of the analysis method defined in Section 6.2.

Change from baseline will be calculated as the visit value of interest minus the baseline value. If the baseline value is missing for a particular variable, then it will not be imputed and the change from baseline and percent change (or percent improvement) from baseline will not be calculated.

For all models, patients will be excluded who do not have the necessary covariates to run the model.

For the primary and key secondary analyses that rely on OS values, the patient's worst ordinal score for the day will be used.

The Per Protocol Set (PPS) will be used if needed for post hoc analyses.

Throughout this document, "Day x" refers to Study Day x.

Additional supportive analyses will be performed as needed.

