### 6.1.2. Definition of Study Baseline

Unless otherwise specified, for efficacy and health outcomes, baseline is defined as the last nonmissing assessment recorded on or prior to, the first date that clinical status is assessed.

Baseline for safety analyses is described in [Table KHAA.6.8](#).

Change from baseline will be calculated as the visit value of interest minus the baseline value. If a baseline value or the value at the visit is missing for a variable, then the change from baseline is defined as missing.

The baseline of vital signs is defined as the vital signs collated at Day 1 from the case report form (CRF) Assessment for the National Early Warning Score (NEWS) (AVPU1001\_VS1001\_F1). The post baseline vital signs for analyses other than NEWS is defined as vital signs collated from CRF Vital Signs: Minimum and Maximum (VS1001).

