### **6.2.1. Logistic Regression Model**

Treatment comparisons of discrete/binary efficacy variables between treatment groups will be made using a logistic regression analysis adjusted for baseline stratification variables (Section 6.1.4). The p-value and odds ratio with 100(1- $\alpha$ )% confidence interval (CI) from the logistic model will be reported.

Point estimates for proportions and difference in proportions will be presented. Confidence intervals and p-values for the estimates of the differences of the proportions and will be presented. For last-observation-carried-forward (LOCF) analyses the CIs will be based on the Newcombe-Wilson method without continuity correction. For multiple imputation analyses, percentages will be based on the observed percentages; CIs will be based on the Wald method without continuity correction.

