### **6.2.2. Analysis of Variance**

Treatment comparisons of quantitative efficacy and health outcome variables will be made using analysis of variance (ANOVA) adjusted for baseline stratification variables (Section 6.1.4). Where appropriate, baseline value for the endpoint of interest will also be included in the model. Type 3 tests for least squares (LS) means will be used for statistical comparison between treatment groups. The LS mean difference, standard error, p-value, and 95% CI will also be reported.

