	5. Hospitalized, requiring supplemental oxygen	Duration of hospitalization	Total number of days patients have a NIAID-OS of 4, 5, 6, or 7. If the patient died on or prior to Day 28, their duration of hospitalization is considered to be 28 days. On Day 1 the patient's worst ordinal scale between baseline and the rest of Day 1 will be used to define their hospitalization status.	Missing if patient's NIAID-OS is missing for any day
	6. Hospitalized, on noninvasive ventilation or high-flow oxygen devices			
7. Hospitalized, on invasive mechanical ventilation or ECMO				
8. Death				

Measure	Description	Variable	Derivation / Comment	Definition of Missing
		All-cause mortality	Time to death by Day 28. Patients included: ITT population Start date: Baseline date Event date: date of death if death is within 28 days of their baseline date. (That is, if baseline is Day 1, any deaths up to and including Day 28 are included). Censor date: Date of last non-missing OS or visit that is on or prior to Day 28. If there is other information that makes it clear that they were alive at Day 28, they will be censored at Day 28.	Missing if the patient's maximum NIAID-OS is not 8 and patient's NIAID-OS is missing for all days after a particular day
Oxygen Saturation	Measure of the oxygen level of the blood measured by pulse oximetry	Oxygen saturation from <94% at baseline to ≥94% (at days 4, 7, 10 and 14)	Patients included: randomized patients whose oxygen saturation (based on NEWS) is < 94% at baseline. A patient is a responder at Day x if their oxygen saturation is ≥ 94% and their OS is not higher than their baseline OS. Otherwise, they are a non-responder. Patients who are missing data at Day x due to having died are considered to be non-responders.	Missing if either baseline or observed oxygen saturation measurement is missing

Abbreviations: ECMO = extracorporeal membrane oxygenation; NIAID-OS = National Institute of Allergy and Infectious Diseases ordinal scale.

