**Table KHAA.6.5. Description of Primary, Key Secondary, and Associated Supportive Analyses**

Measure	Variable	Population	Analysis Method	Time Point	Analysis Type
NIAID-OS	Proportion of patients who died or progressed to non-invasive ventilation or high-flow oxygen (OS $\geq$ 6)	ITT: Population 1 - all randomized patients	Logistic regression using MI	By Day 28	Primary analysis
		ITT: Population 2 – patients who, at baseline, require oxygen supplementation and are not receiving dexamethasone or other systemic corticosteroids for the primary study condition.	Logistic regression using MI	By Day 28	Primary analysis
		ITT	Logistic regression using LOCF	By Day 28	Supportive analysis
		ITT: Population 2	Logistic regression using LOCF	By Day 28	Supportive analysis
		Safety Population	Logistic regression using MI	By Day 28	Supportive Analysis
		ITT Population, excluding patients who die within 24 hours of baseline and have Do Not Resuscitate (DNR) or Do Not Intubate (DNI) orders	Logistic regression using MI	By Day 28	Sensitivity Analysis
		Ventilator free days (VFD)	ITT	ANOVA using MI	By Day 28
	Wilcoxon rank-sum test using LOCF			By Day 28	Supportive analysis
	Proportion of patients with 1-point improvement	ITT	Logistic regression using MI	Day 4, 7, 10, 14	Key secondary analysis
			Logistic regression using LOCF	Day 4, 7, 10, 14	Supportive analysis

Measure	Variable	Population	Analysis Method	Time Point	Analysis Type
	Time to recovery	ITT	Log-rank test using IETI	By Day 28	Key secondary analysis
			Cox proportional hazards model using IETI	By Day 28	Supportive analysis
			Max-combo test using IETI (if needed)	By Day 28	Supportive analysis
NIAID-OS	Overall improvement	ITT	Proportional odds model using MI	Day 4, 7, 10, 14	Key secondary analysis
			Proportional odds model using LOCF	Day 4, 7, 10, 14	Supportive analysis
	Duration of hospitalization	ITT	ANOVA using MI	By Day 28	Key secondary analysis
			Wilcoxon rank-sum test LOCF	By Day 28	Supportive analysis
	All-cause mortality	ITT	Log-rank test	By Day 28	Key secondary analysis
			Cox proportional hazards model	By Day 28	Supportive analysis
Safety					
			Log-rank test	By Day 28	Supportive analysis
			Cox proportional hazards model	By Day 28	Supportive analysis
Oxygen Saturation	Proportion of patients with change in oxygen saturation from <94% at baseline to $\geq$ 94% at the observed time point	ITT	Logistic regression using LOCF	Day 4, 7, 10, 14	Key secondary analysis

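### The key secondary oxygen-saturation model leaves out baseline SpO2, which is known for every analysed patient; the test is valid but may give up some power

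*SAP*

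**What the plan says.** SAP Table KHAA.6.4 (Oxygen Saturation) fixes the analysis set: "Patients included: randomized patients whose oxygen saturation (based on NEWS) is < 94% at baseline". A patient responds on a given day if saturation is at least 94% and "their OS is not higher than their baseline OS". Patients whose value is missing because they died count as non-responders.

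SAP Table KHAA.6.5 lists this as a key secondary endpoint, analysed by logistic regression with LOCF at Days 4, 7, 10 and 14. SAP 6.2.1 describes the model as a "logistic regression analysis adjusted for baseline stratification variables". SAP 6.1.4 lists those variables: baseline OS (4, 5, 6), age group, region and baseline corticosteroid use. SAP 6.3 makes this the default for all models, and nothing different is stated for oxygen saturation. Protocol 9.4.1 gives the same model for dichotomous endpoints.

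The SAP treats an endpoint's own baseline differently elsewhere. SAP 6.2.2, on ANOVA, says: "Where appropriate, baseline value for the endpoint of interest will also be included in the model". The MMRM in SAP 6.2.6 includes baseline and its interaction with day.

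**The concern.** Within one OS level, a patient who starts at 93% and one who starts at 86% probably have different chances of reaching 94%. Baseline OS records the type of oxygen support and does not separate these two patients. The measurement that does is already in the database for everyone analysed, because it decides who enters the set.

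This endpoint also stands apart from the other key secondaries analysed by regression. One-point improvement, overall improvement, ventilator-free days and duration of hospitalization all derive from the NIAID-OS, and baseline OS is a stratification variable. Those models therefore already contain the baseline of their own measure. The oxygen-saturation model does not.

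What is at stake is precision. A logistic model that omits a strong baseline predictor has less power for the treatment effect. Under SAP 6.6 the gated secondaries are tested in sequence and testing stops at the first failure, so lost power here can also affect any endpoint that comes later.

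**Working it through.** **Is baseline SpO2 available for every analysed patient?** SAP 6.1.2 gives its source: "The baseline of vital signs is defined as the vital signs collated at Day 1 from the case report form (CRF) Assessment" for NEWS. SAP 6.1 adds: "If the baseline value is missing for a particular variable, then it will not be imputed". A patient with no baseline SpO2 cannot be shown to be below 94% and so cannot enter the set. Adding the covariate removes nobody.

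**Does the plan give a figure to reproduce?** No. The documents state no number of patients below 94%, no response rate, no effect size and no SpO2 slope for this endpoint. The size has to be illustrated under assumptions.

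**Simulation.** Every input below is an assumption, apart from 1:1 allocation (SAP 5.3) and the one-sided 0.025 level (SAP 6.6).

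- Baseline SpO2 86% to 93%, mean 90.9, SD 1.9, drawn independently of OS.
- 30% at OS 6 and the rest at OS 5; 35% aged 65 or over; 80% on steroids.
- log-odds of response = ln(1.5) × treatment + ln(OR per SpO2 point) × (SpO2 − mean) − 0.8 × OS 6 − 0.4 × age ≥65. A placebo patient under 65 at OS 5 with mean SpO2 thus has a 50% response rate.
- Both models contain treatment, OS, age group and steroid use; one adds SpO2. Region and LOCF were not modelled.
- 2000 trials per setting, Wald test at one-sided 0.025.

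| Total n | SpO2 OR per point | Power without SpO2 | Power with SpO2 | Gain (points) | Estimated OR without / with |
|---|---|---|---|---|---|
| 400 | 1.0 | 50.1% | 49.8% | −0.3 | 1.50 / 1.51 |
| 400 | 1.2 | 48.4% | 50.4% | 2.0 | 1.49 / 1.51 |
| 400 | 1.4 | 43.6% | 46.6% | 3.0 | 1.45 / 1.51 |
| 400 | 1.6 | 39.8% | 45.1% | 5.3 | 1.42 / 1.51 |
| 700 | 1.0 | 71.6% | 71.6% | 0.0 | 1.50 / 1.50 |
| 700 | 1.2 | 71.8% | 72.8% | 1.0 | 1.49 / 1.50 |
| 700 | 1.4 | 66.1% | 69.8% | 3.7 | 1.44 / 1.50 |
| 700 | 1.6 | 60.8% | 68.0% | 7.2 | 1.41 / 1.50 |

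The simulation error of one power figure near 50% is √(0.5 × 0.5 / 2000) = 1.1 points. Both models were fitted to the same data, so the error of a difference is smaller, but it was not computed. Gains of 1 or 2 points should not be read closely.

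**Type I error.** With no treatment effect, rejection rates across all eight settings were 1.9% to 2.9%, with or without SpO2. The simulation error is √(0.025 × 0.975 / 2000) = 0.35 points, so these agree with 2.5%.

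**A second set of assumptions.** With SpO2 84% to 93%, a conditional OR of 1.5, slopes of 0.15, 0.25 and 0.35 log-odds per point and 1500 trials per setting, power rose from 66% to 67%, 62% to 66% and 59% to 64% at n = 600. At n = 400 it rose from 48% to 49%, 45% to 46% and 42% to 47%. These gains are 1 to 5 points, of the same order as in the table.

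**The case against.** The strongest reply is that this is a choice of covariates, not an error. The SAP model matches Protocol 9.4.1, nothing contradicts anything else, and type I error is unaffected. All of that stands.

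The ANOVA sentence concerns quantitative endpoints and is qualified. This endpoint is binary, and its baseline status is the same for everyone in the set, so the inclusion rule already conditions on baseline in part. That is fair: the SAP breaks no rule of its own. It still accepts the principle, and the inclusion rule leaves the spread below 94% unused.

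Baseline SpO2 may also be hard to interpret. Current entry criteria require supplemental oxygen, so a reading may have been taken on support, and 93% on high-flow oxygen is not clearly closer to response than 90% on prongs. OS is in the model and carries some of this. How much SpO2 adds within an OS level cannot be learned from the documents, and the gain may be small or nil.

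Three stronger readings are tempting, and the documents do not support them:

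- **That the odds ratio is biased toward 1.** In a randomised comparison the shift is non-collapsibility. The less-adjusted odds ratio is a different, more attenuated quantity, not a biased estimate.
- **That a miss here brings down a known set of later tests.** The order is in Figure KHAA.6.1, which is not shown, so the knock-on effect cannot be sized.
- **That the change has no downside.** It adds a linearity assumption and goes beyond the protocol's model.

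**Conclusion.** The point holds as a missed gain in precision, and it is minor. The specified analysis is valid. It leaves out a baseline measurement that every analysed patient has and that probably predicts response within an OS level.

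The possible loss is roughly 0 to 7 power points. That range rests wholly on assumed values for the number of patients below 94%, the response rate, the treatment effect and the SpO2 slope. If SpO2 is not prognostic within OS level, nothing is lost. The omission itself is certain from the text; its practical importance is not.

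**What to change.** Before the study team is unblinded, state in SAP 6.2.1 and Table KHAA.6.5 that for the oxygen-saturation endpoint baseline SpO2 (continuous, %) is added to the baseline stratification variables. Use the same model for this endpoint's subgroup analyses in SAP 6.14 and Table KHAA.6.12.

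The cost is one degree of freedom, an assumption of linearity on the log-odds scale, and a short justification for going beyond the model in Protocol 9.4.1. If the covariate is not regarded as a principal feature, Protocol 9.4 allows such a change to be described and justified in the SAP and study report without an amendment. The analysis set and the testing scheme stay as they are. After unblinding, the adjusted model could serve only as a supportive analysis, for which SAP 6.1 already leaves room.

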**Table KHAA.6.5. Description of Primary, Key Secondary, and Associated Supportive Analyses**

Measure	Variable	Population	Analysis Method	Time Point	Analysis Type
NIAID-OS	Proportion of patients who died or progressed to non-invasive ventilation or high-flow oxygen (OS $\geq$ 6)	ITT: Population 1 - all randomized patients	Logistic regression using MI	By Day 28	Primary analysis
		ITT: Population 2 – patients who, at baseline, require oxygen supplementation and are not receiving dexamethasone or other systemic corticosteroids for the primary study condition.	Logistic regression using MI	By Day 28	Primary analysis
		ITT	Logistic regression using LOCF	By Day 28	Supportive analysis
		ITT: Population 2	Logistic regression using LOCF	By Day 28	Supportive analysis
		Safety Population	Logistic regression using MI	By Day 28	Supportive Analysis
		ITT Population, excluding patients who die within 24 hours of baseline and have Do Not Resuscitate (DNR) or Do Not Intubate (DNI) orders	Logistic regression using MI	By Day 28	Sensitivity Analysis
		Ventilator free days (VFD)	ITT	ANOVA using MI	By Day 28
	Wilcoxon rank-sum test using LOCF			By Day 28	Supportive analysis
	Proportion of patients with 1-point improvement	ITT	Logistic regression using MI	Day 4, 7, 10, 14	Key secondary analysis
			Logistic regression using LOCF	Day 4, 7, 10, 14	Supportive analysis

Measure	Variable	Population	Analysis Method	Time Point	Analysis Type
	Time to recovery	ITT	Log-rank test using IETI	By Day 28	Key secondary analysis
			Cox proportional hazards model using IETI	By Day 28	Supportive analysis
			Max-combo test using IETI (if needed)	By Day 28	Supportive analysis
NIAID-OS	Overall improvement	ITT	Proportional odds model using MI	Day 4, 7, 10, 14	Key secondary analysis
			Proportional odds model using LOCF	Day 4, 7, 10, 14	Supportive analysis
	Duration of hospitalization	ITT	ANOVA using MI	By Day 28	Key secondary analysis
			Wilcoxon rank-sum test LOCF	By Day 28	Supportive analysis
	All-cause mortality	ITT	Log-rank test	By Day 28	Key secondary analysis
			Cox proportional hazards model	By Day 28	Supportive analysis
Safety					
			Log-rank test	By Day 28	Supportive analysis
			Cox proportional hazards model	By Day 28	Supportive analysis
Oxygen Saturation	Proportion of patients with change in oxygen saturation from <94% at baseline to $\geq$ 94% at the observed time point	ITT	Logistic regression using LOCF	Day 4, 7, 10, 14	Key secondary analysis

Abbreviations: ANOVA = analysis of variance; IETI = infinite event time imputation; ITT = Intent-to-Treat; MI = multiple imputation; LOCF = last observation carried forward; NIAID-OS = National Institute of Allergy and Infectious Diseases ordinal scale; PPS = Per Protocol Set; VFD = ventilator-free days.

### **6.11.3. Other Secondary Efficacy Analyses**

Table [KHAA.6.6](#) summarizes other secondary efficacy analyses.

Table KHAA.6.6. Description and Derivation of Other Secondary Outcomes

Measure	Variable	Derivation / Comment	Definition of Missing
NIAID-OS	Time to recovery by disease duration of <7 days or $\geq 7$ days prior to enrollment?	Time to reach NIAID-OS 1, 2, or 3 for the first time by disease duration of <7 days or $\geq 7$ days.	Missing if NIAID-OS is missing and time to event of interest cannot be identified using remaining data or the baseline disease duration is missing.
	Time to clinical deterioration	First time patient's observed NIAID-OS – baseline NIAID-OS $\geq 1$	Missing if NIAID-OS is missing and time to event of interest cannot be identified using remaining data.
	Time to clinical improvement in one category	First time patient's baseline NIAID-OS - observed NIAID-OS $\geq 1$ for each NIAID-OS baseline category.	Missing if NIAID-OS is missing and time to event of interest cannot be identified using remaining data.
	Overall improvement	NIAID-OS	Missing if either baseline or observed NIAID-OS is missing.
	Time to independence from noninvasive mechanical ventilation	Patients included: patients whose baseline OS is 6. Start date: Baseline date Event date: First date patient achieves OS 5 or less Censor date (for patients who haven't died but never achieve OS 5 or less by Day 28): Date of last non-missing OS that is on or prior to Day 28. Censor date for patients who die on or prior to Day 28: Date of what would have been their Day 28.	Missing if NIAID-OS is missing and time to event of interest cannot be identified using remaining data.
	Time to independence from oxygen therapy in days	Patients included: patients whose baseline OS is 5 or 6. Start date: baseline date Event date: first date patient achieves OS 4 or less Censor date (for patients who never achieve OS 4 or less by Day 28): Date of last non-missing OS that is on or prior to Day 28. Censor date for patients who die on or prior to Day 28: Date of what would have been their Day 28 visit.	Missing if NIAID-OS is missing and time to event of interest cannot be identified using remaining data.

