**Table KHAA.6.4. Description and Derivation of Primary, Key Secondary, and Associated Supportive Analyses**

Measure	Description	Variable	Derivation / Comment	Definition of Missing
NIAID-OS	Using data from the COVID-19 Clinical Status Assessment, results will be calculated for ordinal scales currently being used in other studies, and in this study, to measure clinical outcomes in patients treated for COVID-19, in particular the NIAID-OS. The NIAID-OS is as follows:	Patients who die or progress to requiring ventilation	Proportion of patients who progress to ventilation or death. In order to be counted as having this event: 
 
• Patients who start at OS 4 or 5 must progress to at least OS 6.
 
• Patients who start at OS 6 must progress to at least OS 7.
 
	Missing if NIAID-OS is missing and the variable status cannot be identified using remaining data.
	1. Not hospitalized, no limitations on activities	Ventilator-free days (days free of invasive mechanical ventilation)	Total number of days patients are alive and have a NIAID-OS less than 7	Missing if patient's NIAID-OS is missing for any day.
	2. Not hospitalized, limitation on activities and/or requiring home oxygen	1-point improvement in OS (at days 4, 7, 10 and 14)	Proportion of patients with baseline NIAID-OS minus NIAID-OS $\geq 1$	Missing if either baseline NIAID-OS is missing or if the observed NIAID-OS is missing on the day of assessment of 1-point improvement
	3. Hospitalized, not requiring supplemental oxygen – no longer requires ongoing medical care: (This would include those kept in hospital for quarantine/infection control, awaiting bed in rehabilitation facility or homecare, etc.)	Time to recovery	Time to reach NIAID-OS 1, 2, or 3 for the first time. The date reached is the first full day that OS 1, 2, or 3 is the patient's maximum OS for the day.	Missing if NIAID-OS is missing and time to event of interest cannot be identified using remaining data
	4. Hospitalized, not requiring supplemental oxygen – requiring ongoing medical care (COVID-19 related or otherwise)	Overall improvement (at days 4, 7, 10, and 14)	NIAID OS	Missing if observed NIAID-OS is missing

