**Description and Derivation of Other Secondary Outcomes**

Measure	Variable	Derivation / Comment	Definition of Missing
	Number of days with supplemental oxygen use	Total number of days patients' NIAID-OS is $\geq 5$	Missing if any observed NIAID-OS is missing.
	Proportion of patients in each severity category	Total proportion of patients in each NIAID-OS category at particular time points	Missing if observed NIAID-OS is missing at particular time point.
	Patients with at least 2-point improvement on the NIAID-OS or live discharge from the hospital	Proportion of patients whose baseline NIAID-OS - observed NIAID-OS $\geq 2$	Missing if observed NIAID-OS is missing or if observed NIAID-OS is $\geq 3$ and baseline NIAID-OS is missing
	Patients with at least 1-point improvement on the NIAID-OS or live discharge from the hospital	Proportion of patients whose observed NIAID-OS is $\leq 2$ or whose baseline NIAID-OS - observed NIAID-OS $\geq 1$	Missing if observed NIAID-OS is missing or if observed NIAID-OS is $\geq 3$ and baseline NIAID-OS is missing
Intensive Care Unit (ICU) stay	Duration of stay in the intensive care unit (ICU)	Total number of days spent in the ICU plus days from death up to and including Day 28.	Missing if status of ICU stay is missing for any day for the patients and the patient is alive.
Fever	Time to resolution of fever	
Time to patients being free of fever for the first time for patients who had fever at baseline.
 
Fever resolution is defined by:
 
 
• <math>\leq 36.6^{\circ}\text{C}</math> (axilla, forehead)
 
• <math>\leq 37.2^{\circ}\text{C}</math> (oral cavity), or
 
• <math>\leq 37.8^{\circ}\text{C}</math> (rectum, ear, temporal artery)
 
 
If temperature is assessed multiple times in a day, fever will be considered to be resolved if all of the measurements fall in the “fever resolution” ranges defined above
	Missing if fever status is missing or baseline fever status is missing and time to event of interest cannot be identified using remaining data.
National Early Warning Score (NEWS)	Mean change	
Mean of observed NEWS – NEWS at baseline
 
NEWS will be calculated using aggregate score approach in Royal College of Physicians [WWW].
	Missing if either baseline or observed NEWS component is missing.

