## Description and Derivation of Other Secondary Outcomes

Measure	Variable	Derivation / Comment	Definition of Missing
Extubation	Time to definitive extubation	
Patients included: randomized patients who progress to OS 7 at any time on or prior to Day 27.
 
Start date: first date that patient progressed to OS 7 (this could be their baseline date if they progressed the first day on study, after baseline)
 
Event date: First date when patient is removed from invasive mechanical ventilation (i.e., OS 6 or less) for the last time on or prior to Day 28.
 
Censor date for patients who are OS 7 at their last observation or by Day 28: Date of last observation.
 
Censor date for patients who die after their Start Date: Date of what would have been their Day 28.
	Missing if NIAID-OS is missing and time to event of interest cannot be identified using remaining data.
Oxygen Saturation	Time to oxygen saturation $\geq 94\%$ on room air in days	
Patients included: randomized patients whose oxygen saturation (based on NEWS) is <math>< 94\%</math> at baseline.
 
Event Date: the first date that their oxygen saturation is <math>\geq 94\%</math> and their OS is <math>\leq 4</math>.
	Missing if NIAID-OS is missing or oxygen saturation status is missing and time to event of interest cannot be identified using remaining data.
Resting respiratory rate	Number of days of resting respiratory rate $< 24$ breaths per minute	
Total number of days when patients' resting respiratory rate <math>< 24</math> breaths per minute.
 
This will be based on values from NEWS.
	Missing if Patient's resting respiratory rate is missing for at least 1 day.

Abbreviations: ICU = intensive care unit; NIAID-OS = National Institute of Allergy and Infectious Diseases ordinal scale.

Table KHAA.6.7. Description of Other Secondary Analyses

Measure	Variable	Population	Analysis Method	Time Point	Analysis Type
NIAID-OS	Time to recovery by disease duration at baseline: < 7 days and ≥7 days	ITT	Log rank test using IETI	By Day 28	Secondary analysis
			Cox Proportional Hazards model using IETI	By Day 28	Supportive analysis
	Time to clinical deterioration	ITT	Log rank test	By Day 28	Secondary analysis
			Cox Proportional Hazards model	By Day 28	Supportive analysis
	Time to clinical improvement in one category	ITT	Log rank test using IETI	By Day 28	Secondary analysis
			Cox Proportional Hazards model using IETI	By Day 28	Supportive analysis

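### Two oxygen endpoints, and marginally a third, score discharge on home oxygen (NIAID-OS 2) as freedom from oxygen

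*SAP*

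**What the plan says.** Three other-secondary endpoints in SAP 6.11.3, Table KHAA.6.6, read oxygen status off the NIAID-OS score:

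- *Time to independence from oxygen therapy.* "Patients included: patients whose baseline OS is 5 or 6"; "Event date: first date patient achieves OS 4 or less".
- *Number of days with supplemental oxygen use.* "Total number of days patients' NIAID-OS is" 5 or more.
- *Time to oxygen saturation of at least 94% on room air.* For patients below 94% at baseline, the event is "the first date that their oxygen saturation is" at least 94% and OS is 4 or lower. The OS condition is the only part of the rule that stands for room air.

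The scale is set out in Protocol 8.1.2 and SAP Table KHAA.6.4, with the same content. State 2 is "Not hospitalized, limitation on activities and/or requiring home oxygen". States 3 and 4 are in hospital without a need for supplemental oxygen.

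**The concern.** The first two endpoints claim by name to measure oxygen therapy, and the third claims room air. Below OS 5, however, one state can still include patients on oxygen. For a patient discharged on home oxygen, the rules record the end of oxygen therapy on a day when only the place of treatment changed. The affected results would then describe oxygen given in hospital while being reported as oxygen use in general.

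Time to recovery also counts OS 2, but that is not the same problem: its definition lists the home-oxygen state openly and does not claim that the patient is off oxygen.

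**Working it through.** The plan gives no figure to reproduce, so the check applies each rule to each state of the scale and then follows one patient.

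**Step 1: states against rules** (SAP Tables KHAA.6.4 and KHAA.6.6).

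| State | On oxygen by definition? | Independence event (OS 4 or lower) | Oxygen day (OS 5 or higher) | Meets OS part of room air |
|---|---|---|---|---|
| OS 1 | Home oxygen is placed in OS 2 | Yes | No | Yes |
| OS 2 | Some patients yes, some no | Yes | No | Yes |
| OS 3, OS 4 | No | Yes | No | Yes |
| OS 5, 6, 7 | On oxygen or ventilatory support | No | Yes | No |

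Only the OS 2 row disagrees with the endpoint names, and only for its home-oxygen part. OS 3 and OS 4 are handled correctly. A patient weaned in hospital reaches the independence event there, before discharge.

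**Step 2: one illustrative patient** (not from the documents). Baseline OS 5, in-hospital oxygen on Days 1 to d, then OS 2 on home oxygen from Day d+1 to Day 28.

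- As written: independence event on Day d+1, and d oxygen days.
- With home oxygen counted as oxygen: no event, censored at Day 28, and 28 oxygen days.
- Undercount, with the SAP 6.1.3 interval formula: 28 − (d+1) + 1 = 28 − d days. For d = 5, 7, 10 and 14 this is 23, 21, 18 and 14 days.

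**Step 3: the room-air endpoint.** It also needs a saturation of at least 94%. The Protocol's Schedule of Activities asks for daily vital signs while the patient is in hospital. After discharge it accepts telephone visits, whose listed contents do not include saturation. A false event therefore needs a reading on or after the first OS 2 day, for example at an on-site visit.

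**Step 4: size within an arm.** If a share h of an arm has m home-oxygen days each, mean oxygen days are understated by h × m. Neither quantity is in the documents, so both are assumptions.

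| h | m = 7 | m = 21 (leaves at Day 7, oxygen to Day 28) |
|---|---|---|
| 5% | 0.35 | 1.05 |
| 10% | 0.7 | 2.1 |
| 20% | 1.4 | 4.2 |

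**Step 5: between arms.** The error in the difference in mean days (baricitinib minus placebo) is −(h × m for baricitinib − h × m for placebo). With 10% and m = 21 in both arms it is −(2.1 − 2.1) = 0. With 10% against 5% it is −(2.1 − 1.05) = −1.05 days, which favours baricitinib. With the shares reversed it is +1.05 days, against baricitinib. The documents give no basis for choosing among these.

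**Step 6: is it repaired elsewhere?** SAP 6.4 allows OS outcomes to be derived from other clinical data, but as a step before imputing missing values; it does not reclassify an observed OS 2. Table KHAA.6.7 lists no analysis that treats home oxygen separately.

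**The case against.** The best defence is that these were meant as in-hospital measures. Protocol 8.1.3 introduces its endpoint table as resting on assessments and procedures in hospitalized patients, and names the NIAID-OS score as the measure of supplemental oxygen use. The SAP follows that method. This explains the choice but does not settle it. The same Protocol row describes use as oxygen by mask or nasal prongs without confining it to inpatients, and none of the endpoint names says in-hospital.

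Three further points stand. The endpoints lie outside the multiplicity scheme in SAP 6.6. The proportion of patients in each OS category is reported at landmark days, so an imbalance in OS 2 would be visible, although its home-oxygen part would not. And in a randomized, double-blind trial, undercounts of similar size in both arms largely cancel in the difference in mean days.

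Stronger readings are tempting:

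- A reader might infer that the trial would credit baricitinib with shortening oxygen dependence when it only moved the oxygen home, or that corrected results would look less favourable. Either needs a difference between arms in discharge on home oxygen, and the documents give none.
- A reader might infer that discharge on oxygen is the expected course because inclusion criterion 4 requires oxygen at entry. Need at entry says nothing about need at discharge.
- A reader might infer that below OS 5 the scale records only site of care. OS 3 and OS 4 show that it does not.

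**Conclusion.** The point holds as a mismatch between definition and name. It is direct for time to independence from oxygen therapy and for days of supplemental oxygen use, and marginal for the room-air endpoint. Only the home-oxygen part of OS 2 is misclassified, and for oxygen independence it matters only for patients who go from OS 5 or above to discharge on oxygen without first reaching OS 3 or 4.

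The within-arm undercount of about 1 to 4 mean days assumes that 5% to 20% of an arm leave at Day 7 and stay on oxygen to Day 28, which is near a worst case; shorter home use gives less. It is not an estimate of bias in the treatment effect, whose direction is unknown. Primary and key secondary tests are untouched. Confidence is high on the definitions and low on the practical impact.

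**What to change.** First establish whether the Clinical Status Assessment records home oxygen as a separate item. The Schedule of Activities says the assessment includes oxygen status, but the case report form is not among the documents.

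- **If it does:** let an OS 2 day count as oxygen-free, for the independence and room-air events, only when home oxygen is recorded as No. Add OS 2 days with home oxygen to the oxygen-use days.
- **If it does not:** rename the first two endpoints *time to independence from in-hospital oxygen* and *days of in-hospital oxygen*. Do not let OS 2 days satisfy room air. Add a sensitivity analysis that counts all OS 2 days as on oxygen. Because OS 2 also holds patients without oxygen, this bounds the effect rather than estimating it.

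Leave the NIAID recovery definition unchanged.

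The cost is wording in three rows of Table KHAA.6.6 and minor programming, with no new data collection. Protocol 9.4 allows analysis changes that are not principal features to be made in the SAP and study report. The main drawback is that oxygen status after discharge may be known only at contacts: Protocol 8.1.1 guarantees only the hospitalization portion daily regardless of contact. The first option therefore needs a stated rule for the days in between. It also needs one for imputed OS 2 days, since the multiple imputation in SAP 6.4.3 generates an OS score and no home-oxygen answer.
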